7.5 Data Collection and Patient Questionnaires

Please refer to [Sections 9.0, 14.0, and 15.0](#) for instructions regarding data collection and patient questionnaires.

7.6 Follow-Up Period

All patients will be followed until 12 months after registration, regardless of whether initial treatment regimen was discontinued or if CSFs were ever used. Refer to [Section 14.4](#) for forms submission requirements.

7.7 Data Reporting

Time points after End of First Cycle are not patient visit driven, but instead are cumulative from date of registration up to the form specified time point. Therefore, the medical record review at the 1 Month, 6 Month and 12 Month time points must happen on or after the patient reaches 1 month, 6 months or 12 months past registration. (Refer to [Sections 9.0](#) and [14.4](#) for Study Calendar and Data Submission information.)

8.0 TOXICITIES TO BE MONITORED AND DOSE MODIFICATIONS

8.1 NCI Common Terminology Criteria for Adverse Events Occurring with Colony Stimulating Factors (CSFs)

This study will utilize the CTCAE (NCI Common Terminology Criteria for Adverse Events) Version 4.0 for toxicity and Serious Adverse Event reporting related to CSFs. A copy of the CTCAE Version 4.0 can be downloaded from the CTEP home page (<http://ctep.cancer.gov>). All appropriate treatment areas should have access to a copy of the CTCAE Version 4.0.

8.2 Dose Modifications

All treatments and dose modifications are at the discretion of the treating investigator, including PP-CSF and systemic therapy.

CLOSED EFFECTIVE 04/15/2020

9.0 STUDY CALENDAR

	Registration	After first cycle of systemic therapy	Mo 1	Mo 6	Mo 12	If initial treatment regimen is discontinued ²	If patient dies
PATIENT QUESTIONNAIRES							
S1415CD Baseline Patient Survey	X						
S1415CD Medical Conditions Questionnaire	X						
S1415CD FACT-N (Version 4)	X	X					
S1415CD Follow-up Patient Survey		X					
S1415CD Use and Copayment Survey				X ³			
SITE COMPLETED FORMS							
S1415CD Registration Worksheet ⁴	X						
S1415CD Onstudy Form	X						
S1415CD Baseline Laboratory Values Form ¹	X						
S1415CD Cover Sheet for Patient-Completed Questionnaires	X	X		X ³			
S1415CD CSF and Cancer Treatment Form		X					
S1415CD CSF Adverse Event Form		X ⁵					
S1415CD Febrile Neutropenia Form		X					
S1415CD Antibiotics Log			X				
S1415CD 6 Month Febrile Neutropenia Log				X			
S1415CD 6 Month Status Update ²				X			
S1415CD 12 Month Status Update ²					X		
S1415CD Discontinuation of Initial Systemic Therapy ²						X	
Notice of Death							X
S1415CD Cause of Death Supplement							X

1. Laboratory tests are not directed by this protocol, however; ANY laboratory results that have been obtained within 28 days prior to registration should be submitted on the **S1415CD** Baseline Laboratories Values Form. Medical records should be closely inspected for baseline leukocytes, ANC, peripheral platelet count and hemoglobin as they are of particular interest to this study.
2. Patients are followed for 12 months, regardless of whether they have discontinued the initial treatment regimen.
3. This survey is due by Month 6, but may be submitted whenever the patient has received the necessary documentation to complete this form. The **S1415CD** Cover Sheet for Patient-Completed Questionnaires should be submitted at the same time the **S1415CD** Use and Copayment Survey is submitted per [Section 15.2f](#).
4. Complete this form prior to patient registration per [Section 13.1](#), but do not submit this form.
5. The CSF Adverse Event Form is required only for those patients who receive CSF during first cycle of initial systemic therapy.

NOTE: Forms are found on the protocol abstract page on the SWOG website (www.swog.org). Forms submission guidelines are found in [Section 14.0](#).

CLOSED/EFFECTIVE 04/15/2020

10.0 CRITERIA FOR EVALUATION AND ENDPOINT ANALYSIS

10.1 Primary Endpoints

- a. Incidence of Febrile Neutropenia (clinical) within six months: Febrile neutropenia as defined by the NCI Common Terminology Criteria for Adverse Events (CTCAE) Version 4.0: absolute neutrophil count (ANC) < 1,000/uL and a single temperature of > 38.3 degrees C (101°F) or a sustained temperature of ≥ 38°C (100.4°F) for more than one hour. (6) Collected at the end of the first cycle on the **S1415CD** Febrile Neutropenia Form and again at six months on the **S1415CD** 6 Month Febrile Neutropenia Log.
- b. Rate of CSF prescribing as primary prophylaxis (clinical) during the first cycle of systemic therapy: Primary prophylaxis of CSF (PP-CSF) is defined as the initiation of granulocyte CSFs during the first cycle of myelosuppressive systemic therapy, given 24 to 72 hours after cessation of systemic therapy, as captured on the **S1415CD** CSF and Cancer Treatment form.
- c. Rate of FN-related emergency department (ED) visits and hospitalizations (clinical) during the first cycle: Admission to ED or hospital with documentation of fever and decreased ANC (see FN definition above), as recorded on the **S1415CD** Febrile Neutropenia form.
- d. Overall survival (clinical): Time from date of registration to date of death due to any cause, using data from the **S1415CD** CSF and Cancer Treatment form, **S1415CD** 6 Month Status Update, **S1415CD** 12 Month Status Update, **S1415CD** Discontinuation of Initial Systemic Therapy form, and the Notice of Death. Patients who are lost to follow-up will be censored.
- e. Prophylactic and FN-related antibiotic use during the first month of therapy (clinical): Outcomes will be measured as total number of antibiotic agents used and duration of antibiotic use, as collected on the **S1415CD** Febrile Neutropenia Form and the **S1415CD** 6 Month Febrile Neutropenia Log.
- f. FN-related HRQL (patient report): Functional Assessment of Cancer Therapy - Febrile Neutropenia (Version 4) (FACT-N). Includes FACT general cancer score and FN-related score. (41,42,43) Evaluated at baseline and at the end of the first cycle of systemic therapy.
- g. Patient adherence to PP-CSF prescription (clinical and patient report) at the end of the first cycle of systemic therapy: Proportion receiving PP-CSF among those for whom PP-CSF was ordered by the physician. The primary adherence measure will be obtained from the patient's chart as reported on the **S1415CD** CSF and Cancer Treatment form; secondary adherence will be measured via self-report on the **S1415CD** Follow-Up Patient Survey.
- h. Patient knowledge of PP-CSF indications, risks, benefits, and out-of-pocket costs (patient report): Evaluated using a patient survey capturing information on PP-CSF that is relevant to informed decision-making (i.e., knowledge of potential benefits, side effects, and short and long-term potential harms, out of pocket costs, and alternative approaches to therapy). Patient knowledge will be evaluated at baseline and at the end of the first cycle of systemic therapy using the **S1415CD** Baseline Patient Survey and the **S1415CD** Follow-Up Patient Survey. Out of pocket costs will be assessed by 6 months after registration based on self-report using the **S1415CD** Use and Copayment Survey.

i. Proportion completing initial systemic therapy regimen: a) at planned duration; b) at planned dose intensity (clinical): Records of early discontinuation or dose modification relative to the initially prescribed regimen will be captured on the **S1415CD** Discontinuation of Initial Systemic Therapy form and the **S1415CD** 12 Month Status Update.

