1.2 Secondary Objective(s)

- a. To compare the rate of FN among low-risk patients registered at Intervention components versus Usual Care components.)
- b. To compare the FN-related health-related quality of life (HRQL) among low-risk patients registered at Intervention components versus Usual Care components.
- c. To compare patient adherence to PP-CSF prescribing among patients registered at Intervention components versus Usual Care components.
- d. To compare patient knowledge of the indications for, efficacy of, and side effects associated with PP-CSF between the initiation and conclusion of the first cycle of myelosuppressive systemic therapy among patients registered at Intervention components versus Usual Care components.
- e. To compare the proportion of patients completing the initial systemic therapy regimen at planned duration and at planned dose intensity among patients registered at Intervention components versus Usual Care components.
- f. To compare antibiotic use both as prophylaxis and as treatment for FN among patients registered at Intervention components versus Usual Care components.
- g. To compare the rate of FN-related emergency department visits and hospitalizations among intermediate risk patients registered to Intervention components by component treatment assignment (administer PP-CSF to intermediate risk patients versus not).
- h. To compare the FN-related health-related quality of life (HRQL) among intermediate risk patients registered to Intervention components by component treatment assignment (administer PP-CSF to intermediate risk patients versus not).
- i. To compare overall survival among intermediate risk patients registered to Intervention components by component treatment assignment (administer PP-CSF to intermediate risk patients versus not).

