What a physician will see if they prescribe an intermediate risk regimen depends on their study arm. If a component is randomized to include standing orders for PP-CSF for all intermediate risk regimens, default PP-CSF orders will appear on the screen in the same way as the default orders for high-risk regimens. If a component is randomized to not include standing orders for PP-CSF for intermediate-risk regimens, the screen will function in the same way as for low-risk regimens. The alert text will be modified to be specific to the intermediate risk classification of the regimen and the randomized assignment.

Order System- Paper

Paper ordering systems will have the same basic design as the EMR modification but will differ in the implementation strategy, as shown below in [Figure 4](#).

INCLUDE CSF by default
 
DOSE-DENSE AC HIGH risk of FN; PP-CSF recommended
 
Height: _____ Weight: _____
 
Chemotherapy Orders:
 
Doxorubicin 75 mg/m² x _____ m²= _____ mg Cyclophosphamide 600 mg/m² x _____ m² = _____ mg
 
Growth Factors: Pegfilgrastim 6 mg subcutaneous
 
Additional Orders: Saline 1000 mL
	
EXCLUDE CSF by default
 
VINORELBINE LOW risk of FN; PP-CSF not recommended
 
Height: _____ Weight: _____
 
Chemotherapy Orders:
 
Vinorelbine 25 mg/m² x _____ m²= _____ mg
 
Additional Orders: Saline 1000 mL

---	--

[Figure 4](#)

The treating physician may change an individual patient's orders from what is specified by following standard procedures for changing a prescription order when adding or removing CSF. The specific procedures will depend on the EMR and local component preference.

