7.3 Process for Assessing Febrile Neutropenia Risk Level

Patients' febrile neutropenia (FN) risk level in the order system will be determined by the febrile neutropenia (FN) risk algorithm developed by the [S1415CD](#) Study Team. The algorithm is based on current NCCN guidelines and peer-reviewed studies, with input from pharmacy and guidelines experts from the investigator team and its external stakeholder advisory group. The algorithm is regimen-based; patient comorbid factors do not inform the algorithm or regimen risk classification at point of order, but will be collected for analysis.

The chemotherapy regimens included in the algorithm are standard breast, non-small cell lung, and colorectal cancer regimens pulled from standard NCCN order templates available on the NCCN website (www.NCCN.org). FN risk is expressed as three different categories: low (<10% risk of FN), intermediate (10-20%), and high (>20%). Risk levels for each regimen are determined by NCCN guidelines and/or peer-reviewed studies. The

list of study recognized regimens and their associated FN risk level is available in [Section 18.1](#).

When a physician orders a particular regimen, the regimen order set will automatically include or exclude CSF based on the FN risk algorithm classification for that regimen and the intermediate risk randomization assignment at that component (see [Figure 1](#) in Section 7.2).

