Step 2: Consider the hypothesis of [Primary Objective b](#): a relative reduction in FN occurrence over 6 months from registration between the Intervention and Usual Care arms (measured by the odds ratio) over both high and intermediate risk groups. We assume FN risk of 25% for the high risk chemotherapy group (translating to a reduction in FN rate from 25% to 12.5%). Using the sample size calculations from Step 1, we employ a 3:1 randomization scheme in the main trial, resulting in 8 components randomized to Usual Care and 24 components randomized to Intervention. This translates to a total of 2,880 patients, 32 components (90 patients per component on average) for the study, and gives us 90% power for [Primary Objective b](#): to detect a 50% reduction in FN events among high and intermediate risk patients in components randomized to the guideline-based PP-CSF order Intervention vs. Usual Care. [Figure 1](#) displays a power curve for our first and second Primary Objectives.

[figure not shown]

Figure 1: Power with respect to the reduction in FN rate. The dashed vertical line is at 50% reduction. The two dashed horizontal lines are at 80% and 90% power.

Table 2 below illustrates how the required sample size for [Primary Objective c](#) and corresponding power for [Primary Objective a](#) vary according to the ICC.

Table 2. Power to detect 50% relative reduction in the FN rate. Power depends on control arm event rate and ICC.

Intra-Class Correlation	Total Sample Size	Per arm sample size		Per arm # of components		Per component sample size		Power	
		Usual Care	Order Entry	Usual Care	Order Entry	Usual Care	Order Entry	Primary Obj b	Primary Obj a
0	1536	384	1152	8	24	48	48	80%	98%
.01	1984	496	1488	8	24	62	62	80%	94%
.02	2880	720	2160	8	24	90	90	80%	90%
.03	5376	1344	4032	8	24	168	168	80%	86%

Using this sample size and with greater than 80% power, we can detect the following effect of Intervention versus Usual Care in the process outcomes of [Primary Objective a](#), namely the proportions of patients using CSF as primary prophylaxis versus other use: a reduction in CSF use from 17% to 7% among low risk patients and an increase in CSF use from 40% to 75% among high-risk patients (based on observed use in our prior observational study). (53)

In addition to the 32 study components, we will include 13 components with existing PP-CSF order entry systems in the parallel cohort to recruit 720 patients (56 patients per component on average).

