11.3 Analysis of Secondary Objectives

- a. *Secondary Objective a: To compare the rate of FN between low-risk patients registered at Intervention components versus Usual Care components.*

The rate of FN will be evaluated at 6 months post-registration. The risk of FN is greatest during the first cycle, but patients are still at risk throughout therapy. The FN risk levels assigned to the various systemic therapies in this protocol are based on risk for the duration of treatment, and so the analysis will look at the FN rate at 6 months into therapy.

A mixed effects logistic model with a random effect for component will be used to assess the effect of prescribing CSFs as primary prophylaxis on FN occurrence within 6 months from registration among low-risk patients. In addition to including an indicator variable for component assignment (Intervention versus Usual Care), we will adjust for component-level characteristics and patient-level clinical and demographic variables.

- b. *Secondary Objective b: To compare the FN-related health-related quality of life (HRQL) between low-risk patients registered at Intervention components versus Usual Care components.*

HRQL is evaluated at the end of the first cycle, the target period for the intervention, while accounting for baseline.

A linear mixed effects model will be fit to assess the effect of the intervention on HRQL, treating the FACT-N score at the follow-up clinic visit as the outcome and adjusting for the baseline FACT-N score. In addition to including an indicator variable for randomized group and a random effect for component, we will adjust for component-level characteristics and patient-level clinical and demographic variables.

- c. *Secondary Objective c: To compare patient adherence to PP-CSF prescribing between patients registered at Intervention components versus Usual Care components.*

PP-CSF is only prescribed during the first cycle, so patient adherence to PP-CSF will be evaluated during the first cycle.

For the home and clinic settings, separate mixed effects logistic models will be used to assess the effect of the intervention on adherence to PP-CSF orders, treating adherence after the start of the study as the outcome. In addition to including an indicator variable for randomized group and a random effect for component, we will adjust for component-level characteristics and patient-level clinical and demographic variables.

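### Adherence is compared only among patients with a PP-CSF order, a group the intervention is designed to change, so the contrast in 11.3c is not an effect of the intervention

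*Combined protocol and SAP*

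**What the plan says.** Section 1.2c sets the objective: "To compare patient adherence to PP-CSF prescribing among patients registered at Intervention components versus Usual Care components". Section 10.1g defines the endpoint as "Proportion receiving PP-CSF among those for whom PP-CSF was ordered by the physician". It stands under the heading for primary endpoints but serves this secondary objective.

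For the analysis, section 11.3c states that for home and clinic settings "separate mixed effects logistic models will be used to assess the effect of the intervention on adherence to PP-CSF orders". The safeguard offered is general: "we will adjust for component-level characteristics and patient-level clinical and demographic variables". FN risk level and the intermediate-risk assignment are not named.

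The intervention acts on the order itself. Under section 7.3, "the regimen order set will automatically include or exclude CSF based on the FN risk algorithm classification". Section 7.2 has CSF on by default for high-risk regimens and off for low-risk regimens. At the 12 of 24 Intervention components assigned to include PP-CSF for intermediate-risk regimens, "default PP-CSF orders will appear on the screen in the same way as the default orders for high-risk regimens"; at the other 12 the default is off. Physicians may override any order.

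Section 11.1 gives the changes the trial should be able to detect: a fall in low-risk use from 17% to 7%, together with "an increase in CSF use from 40% to 75% among high-risk patients".

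**The concern.** Having a PP-CSF order is decided after components are randomised, and it is the variable the intervention is built to move. In Usual Care, the ordered group consists of patients for whom the physician chose CSF. In the Intervention arm it also contains patients who have an order because the default put it there, and it loses patients whose order the default left out. If these patients differ in how often they go on to receive CSF, the arms will differ in adherence even though no patient behaves differently. Section 11.3c would report that difference as something the order system did to adherence.

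Section 11.5 keeps patients in their randomised groups, but it does not deal with an outcome that is undefined for patients without an order. The plan describes no all-patient version and no sensitivity analysis for this selection under Secondary Objective c.

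**Working it through.** **Inputs from the documents.** 720 Usual Care patients in 8 components and 2,160 Intervention patients in 24 (11.1). Risk split 30% high, 50% intermediate, 20% low (11.1). CSF use 40% and 75% (high risk), 17% and 7% (low risk) (11.1). Two-sided alpha 0.05 and ICC 0.02 (11.1). The ICC is stated for FN; carrying it to CSF use and adherence is an assumption.

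**Proxy.** The documents give CSF use, not order rates, so use stands in for orders. If adherence were a common value *a* in both arms, the order rates would be 40/*a* and 75/*a*, and the share in step 2 would not change. True order rates would be somewhat higher than use.

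**1. The plan's own figure.** Section 11.1 claims more than 80% power for the two CSF use contrasts. With a pooled-variance test of two proportions and design effect 1 + (m - 1) x 0.02:
- Low risk: m = 18, 144 vs 432 patients, design effect 1.34, power 82.2%.
- High risk: m = 27, 216 vs 648 patients, design effect 1.52, power above 99.9%.

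Both agree with the claim. The plan states no power for adherence, so no stated figure is in question.

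**2. High-risk patients with an order.** Usual Care: 216 x 0.40 = 86. Intervention: 648 x 0.75 = 486. If everyone ordered under Usual Care would also be ordered under Intervention, (75 - 40)/75 = 47% of the Intervention group would have had no order under Usual Care. This is the minimum. With the least possible overlap, the share is 60/75 = 80%.

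**3. Low-risk patients with an order.** Usual Care: 144 x 0.17 = 24. Intervention: 432 x 0.07 = 30. At least (17 - 7)/17 = 59% of those ordered under Usual Care would have no order under Intervention.

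**4. Risk mix of the ordered groups.** The documents give no intermediate-risk rates. Assume 10% to 50% in Usual Care, and 75% and 7% in the two Intervention halves.
- Usual Care: 86.4 + 360 x (0.10 to 0.50) + 24.5 = 147 to 291 patients, of whom 17% to 8% are low risk.
- Intervention: 486 + 1,080 x (0.75 + 0.07)/2 + 30.2 = 959 patients, of whom 3% are low risk.

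**5. Apparent difference from selection alone, high risk.** Let A be adherence in always-ordered patients and N adherence in newly ordered patients, both unaffected by arm. Usual Care shows A. With the minimum share from step 2, Intervention shows (40A + 35N)/75. All values of A and N are assumed.

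| A | N | Usual Care | Intervention | Difference (points) | Odds ratio | Chance of p < 0.05 |
|---|---|---|---|---|---|---|
| 95% | 95% | 95.0% | 95.0% | 0.0 | 1.00 | 5% |
| 95% | 90% | 95.0% | 92.7% | -2.3 | 0.67 | 8% |
| 95% | 85% | 95.0% | 90.3% | -4.7 | 0.49 | 20% |
| 95% | 80% | 95.0% | 88.0% | -7.0 | 0.39 | 39% |
| 85% | 95% | 85.0% | 89.7% | +4.7 | 1.53 | 24% |

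The last column is a normal approximation with 86.4 and 486 ordered patients and design effects 1 + 9.8 x 0.02 = 1.196 and 1 + 19.25 x 0.02 = 1.385. It pools home and clinic settings.

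**The case against.** Adherence has meaning only for a patient who has an order, so 10.1g is the natural definition, and replacing it with ordered-and-received among everyone would change the question. The randomised question about receipt is already answered: PP-CSF is defined by administration, and 11.2a fits separate models of its use to all high-risk and all low-risk patients. FN risk follows from the regimen and could be counted among the clinical variables adjusted for; comorbid factors are collected as well. Because physicians can override the default, an order left in place reflects some acceptance. Finally, this is one of nine secondary objectives, with no stated hypothesis or power, and no primary conclusion depends on it.

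Much of this stands. The endpoint should be kept, no new formal outcome is needed, and adjusting for FN risk level would remove the imbalance in risk mix. It would not remove differences within a risk level between patients whose physician chose CSF and patients with an order only by default. Whether the unnamed general covariates would capture those differences is not shown. The objection does not rescue the wording in 11.3c that presents the ordered-only model as an effect of the intervention.

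A reader might also infer that splitting the models by home and clinic adds a bias of its own. The documents do not support that: nothing in them says the default changes the setting, and choice of CSF product is left to the physician.

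**Conclusion.** The point holds as one of interpretation and labelling. The ordered groups are not comparable by randomisation, and the plan's own figures imply a large change in membership: at least 47% of ordered high-risk Intervention patients would have had no order under Usual Care, with use standing in for orders. The low-risk share of orders is higher in Usual Care, 8% to 17% against 3% under the assumed intermediate-risk rates.

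A reader might go further in three ways that the documents do not support.
- That adherence will appear about 7 points lower under the intervention. That figure needs assumed rates of 95% and 80%. The bias is zero if the two groups adhere equally, and positive if newly ordered patients adhere better.
- That 47% is a ceiling. It is a floor, reached only when everyone ordered under Usual Care is also ordered under Intervention.
- That low-risk patients are 22% of ordered patients in Usual Care against 6% in Intervention. Those shares come from high- and low-risk orders alone (24.5/110.9 and 30.2/516.2) and leave out intermediate-risk patients, half the planned sample.

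The calculation uses the planned risk mix. Section 5.2b later limits randomised sites to intermediate-risk registrations, so the achieved mix may differ.

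**What to change.** In 11.3c:
- Report adherence among ordered patients by arm within FN risk level and, for intermediate risk, by the components' PP-CSF assignment. If a single model is kept, include these terms as a minimum. State that the comparison is descriptive and is not an estimate of the intervention's effect.
- For the randomised contrast, refer to the PP-CSF use models under Primary Objective a, and show beside them, by arm, the two components: the proportion ordered, and the proportion received given an order. Those models cover high- and low-risk patients only, so intermediate-risk adherence stays descriptive.
- Show home and clinic settings as a descriptive table.

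The objective in 1.2c and the definition in 10.1g can stay as they are. The change is to analysis and reporting wording; 10.1g already takes its primary adherence measure from the CSF and Cancer Treatment form. The cost is that the ordered-only comparison loses its causal interpretation and its p-value. Some cells will also be small: about 24 low-risk patients with an order in Usual Care on the plan's figures.
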